5.4 Demographic Characteristics

A table describing baseline conditions and demographics of the study population, including baseline distribution of FcγRIIa, will be provided. In addition, correlations between baseline FcγRIIa and other baseline subject characteristics will be calculated and displayed in scatterplots and boxplots, as appropriate.

5.5 Disease Characteristics Associated with Increased Cardiovascular Risk

We will use clinical characteristics that have been associated with greater risk of subsequent cardiovascular events (MI, stroke, death) in our planned secondary analysis. These clinical characteristics have been derived from large clinical trials (see references).

5.6 Objectives and Endpoints

The primary objective of the study is to determine whether platelet expression of FcγRIIa is associated with risk of MI, stroke, and death.

Secondary objectives are:

- Develop a score that combines clinical characteristics plus platelet expression of FcγRIIa to determine the risk of MI, stroke, and death.
- Determine whether platelet expression of FcγRIIa is associated with risk of major bleeding.

The primary endpoint is the composite of death, MI, and stroke. A secondary endpoint is clinically significant bleeding according to BARC type 2-5.

5.7 Statistical Methods

5.7.1 Analysis of the Primary Objective

The primary analysis of the primary endpoint will be a Cox proportional hazards model. The dependent variable is the number of days from enrolment to the occurrence of a primary endpoint, with censoring at the last day of complete follow-up; independent variables will be FcγRIIa (measured in thousands), age in years, history of diabetes mellitus, prior revascularization, multi-vessel coronary artery disease (MVD) defined as ≥2 vessels or left main with a stenosis ≥50%, chronic kidney disease (CKD) defined as estimated glomerular filtration rate (GFR) < 60 ml/min/1.73 m², prior MI, hypertension, tobacco use, heart failure or LVEF<30%, previous stroke or transient ischemic attack, and peripheral arterial disease. Interest is in the FcγRIIa parameter: point estimate (increase in risk per 1000-unit increase in FcγRIIa), confidence interval and p-value. FcγRIIa will be declared to be associated with cardiovascular risk if the 2-sided p-value from this model is < 0.05.

A set of exploratory/sensitivity and subgroup analyses based on the Cox model will also be conducted.

- Instead of censoring at the last day of complete follow-up, censor at the last day of vital status follow-up
- FcγRIIa as the only covariate in the model
- Separate analyses of each component of the primary endpoint: MI and stroke, both censored at the last day of complete follow-up, and death, censored at the last day of vital status follow-up
- Run the primary model in subgroups defined by age (in decades), sex, history of diabetes and prior revascularization (including all covariates except the subgroup variable in the model)
- Run the primary model with the use of DAPT (any use prior to a primary endpoint), and its interaction with FcγRIIa, as additional covariates

A final set of exploratory analyses will be done to help determine the optimal threshold value of FcγRIIa for risk stratification. Define a threshold value, x, and define “low” FcγRIIa as a value less than or equal to x, and “high” FcγRIIa as a value greater than x. Next, calculate exposure-adjusted subject incidence rates for the primary endpoint, separately for the “low” and “high” subgroups, as the number of subjects with an event divided by the sum across subjects of the event/censoring times. Then, plot the exposure-adjusted incidence rates as a function of x for each subgroup, as well as the difference between subgroups. In addition, ROC curves will be produced showing the sensitivity and specificity of FcγRIIa to predict the presence or absence of a primary endpoint, as a function of the FcγRIIa threshold.

Flow cytometry considerations

[figure not shown]
Flow cytometry output, mean fluorescence intensity (MFI), can be influenced by multiple factors. External standards are used to translate MFI into molecules/platelet. In the original study, Bangs Laboratories Quantum MESF beads were used to translate MFI to antibody binding capacity ([name] et al). Because our antibody is labeled with 1 molecule of phycoerythrin (PE) per antibody, the antibody binding capacity equates to molecules per platelet.

Shortly before initiating the current study, Bangs Laboratory changed their calculation template. The company reported that over time their calculation template had experienced a shift (personal communication). This change led to a substantial change in the quantification. The change represents a ‘unit’ change rather than a complete revision of the translation of MFI into molecules/platelet.

Results using Bangs Laboratories Quantum MESF were compared with an independent external standard, BD Quantibrite. The two external standards (Quantum MESF and Quantibrite) yielded similar results. Based on this information, the revision of the formula by Bangs Laboratories was determined to be a more accurate assessment of molecules/platelet.

Results from the original study were analyzed with the use of the Quantibrite formula to relate results obtained using the previous Bangs Laboratories formula with the formula used with Quantibrite beads.

A nearly perfect fit is obtained with log-transformation of the data. The plotted values are the natural logs of the original values. This regression line also doesn't go through zero (see the expanded scale), so the regression line is as follows: $\log(\text{Quantibrite}) = a * \log(\text{Original Bangs}) + b$, where $a = 0.9160084$ and $b = -1.0611595$.

The relationship derived was used to translate the original threshold of 11,000 to a new threshold that will be tested in this study. A value of 11,000 obtained with the original calculation template provided by Bangs Beads corresponds to a Quantibrite value of $\exp(a * \log(11,000) + b) = 1742.183$. Thus, we will use a threshold rounded to the closest 50, or 1,750, to define subjects with low versus high Fc γ RIIa.

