Platelets from healthy young people carry 1,000-4,000 molecules of FcγRIIa (Karas 1982). Calverley and colleagues found that platelet expression of FcγRIIa was increased in patients with an acute coronary or cerebrovascular events as well as in patients with diabetes and individuals without cardiovascular events who had two or more cardiac risk factors (Calverley 2002). In addition, they found limited intra-individual variability when repeat determination was performed after 6-52 (average 20) weeks (Calverley 2002). These results suggest that, unlike measures of platelet function that exhibit marked intra-individual variability (Frelinger 2013, Hochholzer 2014, Nührenberg 2015), platelet expression of FcγRIIa is a consistent marker of increased platelet reactivity.

Flow cytometry is a powerful tool capable of assessing expression of FcγRIIa on the platelet surface. Platelets are identified by their size as well as a surface marker. Without a standardized measure of fluorescence intensity, results of analyses can be described only in relative terms of fluorescence intensity. The interpretation of fluorescence intensity measurements can be complicated by multiple factors including daily instrument variation, differences in hardware (laser power, filter sets), as well as the density of fluorochrome labeling of antibodies. A goal is to develop a clinically validated tool that can be used broadly in the care of patients, therefore external standards will be employed in the current study to enable the standardization of fluorescence intensity units (Kay 2006, Quadrini 2016). Accordingly, platelet expression of FcγRIIa will be quantified with the use of external standards to quantify the number of molecules on the platelet surface rather than relative platelet expression of FcγRIIa.

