## 8 STUDY ASSESSMENTS AND PROCEDURES

### 8.1 EFFICACY AND SAFETY ASSESSMENTS

This is an observational non-interventional study, therefore there is no evaluation of efficacy or safety. Blood will be taken prior to discharge from the hospital for the index MI event (see separate Laboratory Sample Manual for details on sample collection, storage, and shipment to a core laboratory) and will be used to quantify FcγRIIa. Blood can be taken up to 2 weeks post-study enrollment. Risks associated with phlebotomy include discomfort, bleeding, and a remote risk of infection.

Subjects will receive medications as determined by their health care provider and as part of regular standard of care. Subjects will be followed throughout the duration of the study to assess for study endpoints including MI, stroke, death, and bleeding events (BARC type 2-5). Subjects who experience an endpoint event will continue to be followed throughout the entire study and any subsequent events will also be confirmed and recorded.

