### 9.3 POPULATION FOR ANALYSES

All enrolled subjects who are eligible based on the inclusion/exclusion criteria will be included in the population for analysis.

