#### 9.4.2 ANALYSIS OF THE PRIMARY OBJECTIVE

Cox proportional hazards models will be fit to compare the risk of the primary endpoint based on platelet expression of FcγRIIa as a continuous variable. Subjects will be followed until their earliest MI, stroke, or death. Patients who do not experience the composite endpoint will be censored at their last telephone follow-up. Time to the primary endpoint will be calculated as days from study enrollment. Models will be adjusted for potential confounders including sex and other subject demographics and medical history collected at baseline. In the pilot study, it was observed that older age, diabetes mellitus, and prior revascularization were associated with higher platelet FcγRIIa expression.

A set of sensitivity analyses will evaluate FcγRIIa as a binary endpoint, which each analysis using a different threshold for classifying FcγRIIa as high or low. In particular, these analyses will explore whether a binary or a continuous measure of FcγRIIa provides greater predictive value, and whether or not a threshold of  $\geq 11,000/\text{platelet}$  is optimal.

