5.8 Safety Data

The only safety information collected in this study is serious adverse events associated with the venipuncture that takes place on Day 1. All adverse events will be listed and, if there is a meaningful number of them, tabulated as well.

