5.9 Handling of Missing and Incomplete Data

Subjects with missing data for baseline FcγRIIa will be excluded from all analyses. Missing values for other covariates will be imputed using a median value imputation for continuous variables and most frequent value imputation for categorical variables.

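### The event clock starts at enrolment, but FcγRIIa may be sampled up to 2 weeks later and no rule covers events in between; the gap is real, its expected effect small

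*SAP*

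**What the plan says.** **Time origin.** SAP 5.7.1: "The dependent variable is the number of days from enrolment to the occurrence of a primary endpoint". Protocol 9.4.2 agrees: "Time to the primary endpoint will be calculated as days from study enrollment".

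**Marker sampling.** Protocol 8.1 gives the default, "Blood will be taken prior to discharge from the hospital for the index MI event", and then the allowance, "Blood can be taken up to 2 weeks post-study enrollment". The same allowance stands in Protocol 1.3 (footnote b) and 4.1. The revision history shows that version 4.0 introduced it. The time origin remains enrolment.

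**The SAP's view of the draw.** SAP 5.8 speaks of "serious adverse events associated with the venipuncture that takes place on Day 1", and SAP 5.2 treats Day 1 as the only in-person visit. The 2-week window does not appear in the SAP.

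**Subjects without a value.** SAP 5.9: "Subjects with missing data for baseline FcγRIIa will be excluded from all analyses". Protocol 9.3 reads differently: "All enrolled subjects who are eligible based on the inclusion/exclusion criteria will be included in the population for analysis".

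**What is absent.** Neither document sets delayed entry, a landmark, or a rule for events dated before the sample. The additional analyses in SAP 5.7.1 vary the censoring date, the covariates, the endpoint component, the subgroup and DAPT use. None of them varies the start of time at risk.

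**The concern.** A prognostic analysis should relate a marker to events that come after its measurement. Here the marker can be measured after the clock has started, which has two consequences for subjects with a delayed draw.

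- **Death before the draw.** No value exists, so the subject and a primary-endpoint death both leave the analysis. Every late-sampled subject who is analysed must have survived to the draw, so those days are immortal time.
- **Non-fatal event before the draw.** The subject stays in, and the event is set against a baseline value obtained after it.

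The second consequence raises the possibility of reverse causation, because the protocol's background section reports that "platelet expression of FcγRIIa was increased in patients with an acute coronary or cerebrovascular events". The bleeding model in SAP 5.7.2 reuses the primary model and inherits the problem. Pre-sample events also enter the incidence-rate plots, the ROC curves and the predictive values.

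**Working it through.** The documents give no figure for events between enrolment and the draw, so there is none to reproduce.

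**1. Two subjects followed through the rules (invented dates)**
- Enrolled day 0, draw planned for day 10, dies on day 8: no FcγRIIa value, so SAP 5.9 excludes the subject and the death is not counted.
- Enrolled day 0, MI on day 6, sampled on day 10: the event time is 6 days and the covariate was measured 4 days after the event.

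**2. Events in the window**

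Inputs: N = 800 (SAP 5.10); hazard h = 0.10 per year (Protocol 4.1); window 14 days (Protocol 8.1). The share of delayed draws f and any early excess hazard are not given, so the values used are assumptions.

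If delayed draws all fall on day 14, expected events before the draw = N × f × (1 − exp(−h × 14/365)). If they are spread evenly over days 0 to 14, this is averaged over the window.

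| Early hazard | All delayed, day 14 | All delayed, even spread | 25% delayed, day 14 | 25% delayed, even spread |
|---|---|---|---|---|
| 10% per year | 3.06 | 1.53 | 0.77 | 0.38 |
| 3 times that (assumption) | 9.15 | 4.59 | 2.29 | 1.15 |

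First cell: 800 × (1 − exp(−0.10 × 14/365)) = 3.06. With the registry rate of 9.7 per 100 patient-years (Protocol 2.3) it is 2.97.

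**3. Total events for comparison**

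The study stops only when there are at least 80 events and the last subject has 18 months of follow-up (Protocol 4.2). With 12 months of enrolment, follow-up runs from 1.5 to 2.5 years, about 2 on average: 800 × (1 − exp(−0.10 × 2)) = 145 events, ignoring dropout.
- 3.06 events are 3.8% of 80, or 2.1% of 145.
- 9.15 events are 11.4% of 80, or 6.3% of 145.

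**4. Effect on the estimate**

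A Cox simulation compared the enrolment clock with delayed entry at the draw (400 runs per scenario, 800 subjects, continuous marker). It assumed that 40% of events are fatal and that delayed draws are spread evenly over the window.
- The most adverse scenario had a 3-fold early hazard, all draws delayed, and the marker raised by 1 SD after a non-fatal pre-draw event. About 1.9 deaths were lost and 2.8 non-fatal events preceded the draw, out of about 150 events.
- With no true association, the enrolment-clock hazard ratio was at most 1.013 per SD in any scenario. Type I error was 4.5% to 5.5%. The simulation error is about 1.1 points: √(0.05 × 0.95/400).
- With a true hazard ratio of 1.40 per SD, estimates were 1.39 to 1.42 on the enrolment clock and 1.39 to 1.40 with delayed entry.

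The delayed-entry arm dropped subjects with a pre-draw event altogether. The fix below keeps them at risk for later events, a difference of only a few subjects.

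**5. Power cost of discarding early events**

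Schoenfeld formula, hazard ratio 2, equal groups, two-sided 0.05: power = Φ(√(D/4) × ln 2 − 1.96).
- D = 80: 87.3%
- D = 77: 86.0%
- D = 71: 83.2%

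These figures only show the loss. SAP 5.10 states at least 95% power at a two-sided level below 0.01. That does not reproduce (64 events, which is 8% of 800, give 57.8% at 0.01), but it is a separate matter with no bearing on this point.

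**The case against.** The case for leaving the plan alone is a good one on size.

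- Sampling before discharge is the default, so many subjects may have no gap at all.
- The marker is described as stable: a change below 10% over 2 to 6 weeks in healthy subjects (Protocol 4.3), and an average change below 10% over 6 to 52 weeks in 248 cardiovascular patients (Protocol 2.3).
- In the pilot, the risk groups separated only after 6 months.
- At most 14 death-free days, against at least 18 months of follow-up, bias the FcγRIIa coefficient materially only if draw delay or pre-draw death is related to the marker. Nothing in the documents shows that.

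All of this stands as an argument that the effect is small. It does not close the gap. Neither stability result is described as spanning a new MI or stroke, consistency in this cohort is what the substudy sets out to demonstrate, and the share of delayed draws is unknown.

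Three stronger readings are tempting but unsupported.

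- **That early deaths in general drop out.** Only deaths before a delayed draw do.
- **That a new event raises the marker and so inflates the hazard ratio.** The background result compares patient groups; it does not show a rise within days of an event. Every subject here has already had an acute MI, so all values are post-event. Reverse causation is plausible, not demonstrated.
- **That the bias could be large.** A reader might split 80 events 40/40 and put 5 or 9 pre-sample events on the high side, giving 45/40 = 1.13 or 49/40 = 1.23. The count of 9 includes deaths, which the missing-value rule removes. Nothing supports placing every event on the high side. The figure of 80 is a minimum against about 145 expected. The primary model also uses FcγRIIa as a continuous variable.

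**Conclusion.** The point holds as a specification gap. For subjects with a delayed draw, the plan credits death-free time by construction, loses pre-draw deaths, and counts non-fatal events that precede the marker meant to predict them. This follows from the text without any assumption.

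The size is small: at most about 3 primary events at the protocol's own rate, and fewer than 1 if a quarter of draws are delayed. The figure of about 9 needs both an assumed 3-fold early hazard and every draw on day 14. The simulations do not suggest a threat to the primary conclusion. The change is still worth making because it is cheap and removes an avoidable objection to a prognostic claim.

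**What to change.** In SAP 5.7.1 and 5.7.2 and Protocol 9.4.2 and 9.4.3:

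1. Keep the enrolment time scale, with delayed entry on the date of the FcγRIIa sample used in the analysis. Resetting the clock to zero at the sample is a different time scale with different risk sets, so the text should name the one chosen.
2. Count only events after the sample. State that a subject with a non-fatal event before it stays at risk for the first event after it.
3. Apply the same rule to the bleeding model, the incidence-rate plots (person-time from the sample), the ROC curves and the predictive values.
4. Tabulate deaths and non-fatal events before the sample. The fix does not recover those deaths, because they have no marker value; the table makes them visible.
5. Run the enrolment clock as a sensitivity analysis.
6. Align SAP 5.8 with the protocol's 2-week window, and reconcile SAP 5.9 with Protocol 9.3 on who is analysed.
7. Confirm that the sample date is captured. Neither document says so expressly.

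**Cost.** Wording changes in both documents, plus a few early events leaving the primary analysis. With 80 events, power for a hazard ratio of 2 at two-sided 0.05 falls from 87.3% to 86.0% if 3 are lost, or to 83.2% if 9 are lost.

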### 9.4 STATISTICAL ANALYSES

#### 9.4.1 GENERAL APPROACH

The planned statistical analyses will be included in a study Statistical Analysis Plan (SAP).

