#### 9.4.3 ANALYSIS OF THE SECONDARY OBJECTIVES

First Secondary Objective: Negative predictive value, positive predictive value, sensitivity, and specificity will be calculated. Prediction will be performed using a Cox regression model with the following predictors: platelet expression of FcγRIIa, sex, age, MVD, CKD, DM, and prior MI. Evaluation of the model's error rates will be based on a leave-one-out cross-validation approach. Additional models will evaluate the performance of the predictive model using a continuous measure of FcγRIIa with the performance of predictive models using various binary measures of FcγRIIa.

Second Secondary Objective: The adjusted Cox proportional hazards model described for the primary objective analysis will be used to compare the bleeding risk as a function of FcγRIIa expression, both as a continuous and as a binary variable.

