5.7.2 Analysis of the Secondary Objective

First Secondary Objective: Negative predictive value, positive predictive value, sensitivity, and specificity will be calculated. Prediction will be performed using a Cox regression model with the following predictors: platelet expression of Fc γ RIIa, sex, age, and clinical risk factors associated with increased cardiovascular risk. Evaluation of the model's error rates will be based on a leave-one-out cross-validation approach. Additional models will evaluate the performance of the predictive model using a continuous measure of Fc γ RIIa with the performance of predictive models using various binary measures of Fc γ RIIa.

Second Secondary Objective: The adjusted Cox proportional hazards model described for the primary objective analysis will be used to compare the bleeding risk as a function of Fc γ RIIa expression. One

model will include FcγRIIa as a continuous variable, and another using the dichotomized version of FcγRIIa selected as the optimal version for risk stratification.

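### The protocol says the primary Cox models will be adjusted for sex, but the SAP's covariate list for the primary model leaves sex out

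*SAP*

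**What the plan says.** Protocol 9.4.2, on the primary objective, states: "Models will be adjusted for potential confounders including sex and other subject demographics and medical history collected at baseline". Protocol 9.4.1 leaves the planned analyses to the SAP.

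SAP 5.7.1 lists the independent variables of the primary Cox model: FcγRIIa in thousands, age, diabetes, prior revascularization, multi-vessel disease, chronic kidney disease, and then "prior MI, hypertension, tobacco use, heart failure or LVEF<30%, previous stroke or transient ischemic attack, and peripheral arterial disease". The list is closed; nothing in it lets further covariates be added. FcγRIIa will be "declared to be associated with cardiovascular risk if the 2-sided p-value from this model is < 0.05".

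Sex appears elsewhere in the plan:

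- **Subgroups (SAP 5.7.1):** "Run the primary model in subgroups defined by age (in decades), sex, history of diabetes and prior revascularization", with the instruction "including all covariates except the subgroup variable in the model".
- **Prediction model:** protocol 9.4.3 uses FcγRIIa with "sex, age, MVD, CKD, DM, and prior MI"; SAP 5.7.2 uses FcγRIIa with "sex, age, and clinical risk factors associated with increased cardiovascular risk".
- **Bleeding (SAP 5.7.2):** the analysis reuses the adjusted model of the primary objective, so it takes over that model's covariates.

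**The concern.** The model that decides the primary objective lacks the covariate that the protocol's adjustment sentence names. The FcγRIIa hazard ratio would be reported as adjusted, but not for sex, for both the primary endpoint and bleeding. The sensitivity analyses built on the primary model inherit the same list.

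Pre-specification is also at stake. An analyst who follows the SAP fits 12 terms; one who follows the protocol sentence adds sex. Both can cite a governing document. If the mismatch is noticed only after the data are open, there are two defensible primary p-values and no rule for choosing between them.

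**Working it through.** **1. Compare the lists.**

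| Model | Sex included? |
|---|---|
| Primary Cox model, protocol 9.4.2 | Yes, by name |
| Primary Cox model, SAP 5.7.1 | No |
| Sex subgroup runs, SAP 5.7.1 | By stratification only |
| Bleeding model, SAP 5.7.2 | No (inherited from the primary model) |
| Prediction model, protocol 9.4.3 and SAP 5.7.2 | Yes, by name |

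The terms in SAP 5.7.1 are FcγRIIa, age, diabetes, prior revascularization, multi-vessel disease, kidney disease, prior MI, hypertension, tobacco use, heart failure or low LVEF, stroke or TIA, and peripheral arterial disease. That is 12 terms, counting tobacco as one because its coding is not stated. With sex there are 13.

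**2. Check the subgroup instruction.** It names four variables and says to leave the subgroup variable out of the model. Age, diabetes and prior revascularization are in the list. Sex is the only one of the four that is not, so for sex there is nothing to leave out.

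**3. Check the stated predictor budget (SAP 5.10).** 80 events / 10 per predictor = 8 predictors, which reproduces the plan's FcγRIIa plus seven. The list as written already exceeds this: 80/12 = 6.67 events per term, or 80/13 = 6.15 with sex. At 10 per term, 13 terms need 130 events.

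**4. Expected first events.** Inputs from the protocol synopsis and 4.1: 800 subjects, 12 months of enrollment, at least 18 months of follow-up after the last subject, and a 10% annual event rate. Assumed here: uniform accrual, a constant hazard of 0.10 per year, cutoff at month 30 and no dropout.

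- Mean event probability = average over u from 0 to 1 of 1 − exp(−0.10 × (2.5 − u)) = 0.1809
- 800 × 0.1809 = 144.7 events
- If 10% lack an FcγRIIa value (assumed; SAP 5.9 excludes them): 720 × 0.1809 = 130.3 events

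**5. Shift in the FcγRIIa estimate when sex is omitted.** The documents give no sex effect. Assumed: sex HR 1.2 to 1.5; partial correlation r between sex and FcγRIIa of 0 to 0.2; 30% women, so SD(sex) = √(0.3 × 0.7) = 0.458.

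Shift in log HR per SD of FcγRIIa ≈ ln(HR_sex) × r × SD(sex). SE per SD ≈ 1/√events: 0.083 at 145 events, 0.088 at 130, 0.112 at 80. The last column takes a result sitting exactly at p=0.05 (z=1.96), moves it by the shift in either direction, and uses 145 events.

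| Sex HR | r | Shift | HR factor | Shift in SE, 145 events | p=0.05 becomes |
|---|---|---|---|---|---|
| any | 0 | 0 | 1.00 | 0 | 0.05 |
| 1.2 | 0.1 | 0.0084 | 1.008 | 0.10 | 0.063 or 0.039 |
| 1.3 | 0.1 | 0.0120 | 1.012 | 0.14 | 0.070 or 0.035 |
| 1.5 | 0.2 | 0.0372 | 1.038 | 0.45 | 0.13 or 0.016 |

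At the top of the range the shift is 0.42 SE with 130 events (p=0.05 becomes 0.12 or 0.017) and 0.33 SE with 80 events. With 25% or 40% women the factor is 1.036 or 1.041.

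**6. Precision cost of adding sex.** SE inflation = 1/√(1 − r²): 1.005 at r=0.1 and 1.021 at r=0.2. A simulation with 400 runs, n=800, FcγRIIa HR 1.3 per SD, sex HR 1.5 and r=0.2 gave a mean shift of 0.040 and an SE ratio of 1.021, in line with the formulas.

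**The case against.** **The omission may be deliberate.** Protocol 9.4.1 lets the SAP settle the analysis, and the available SAP text begins at 5.1, so a rationale could stand in a part not seen. The subgroup instruction is one generic phrase that simply removes nothing for sex. This stands in part: the text suggests an oversight but does not prove one. It does not remove the conflict, and the fix allows for a deliberate choice.

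**There is no sign that sex confounds.** Protocol 2.3 reports the pilot groups as balanced except for age, diabetes and prior revascularization, and all three are in the SAP model. This stands as a limit on the size. However, the pilot had 197 patients, the protocol does not say that sex was among the characteristics compared, and adjustment for sex was promised anyway.

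**The plan already handles sex in part.** SAP 5.4 relates FcγRIIa to other baseline characteristics, which could show a link with sex. The runs within each sex remove confounding by sex from those estimates. The prediction model would yield a sex-adjusted FcγRIIa coefficient, although its planned outputs are predictive values, sensitivity and specificity. All of this helps, but none of it carries the p<0.05 rule.

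**The model is already too large.** The list exceeds the eight-predictor budget, and sex would add a thirteenth term. That should be disclosed. But the guideline is stated for building the prediction model, it did not keep out hypertension, tobacco use or peripheral arterial disease, and about 130 to 145 expected events would meet it with 13 terms.

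**Conclusion.** The concern holds. The mismatch between protocol 9.4.2 and SAP 5.7.1 is certain from the text, and it sits in the model that decides the primary objective and is reused for bleeding. Its cause is not known.

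The effect on the FcγRIIa hazard ratio is also unknown and probably small: none if sex and FcγRIIa are unrelated given the other covariates, and a factor of about 1.04 per SD at the top of the assumed range. The declaration would change only for a result near p=0.05. The p-values of 0.13 and 0.016 belong to the extreme corner of that range; milder assumptions move p=0.05 only to about 0.06 to 0.07, or 0.035 to 0.04. The effect on the bleeding estimate was not sized.

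This should be put right, chiefly to keep the primary analysis unambiguous.

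**What to change.** Before results are seen, add sex to the independent variables in SAP 5.7.1, directly after age, giving 13 terms. Sex then becomes the term left out in the sex subgroups, which makes that instruction work for all four variables. SAP 5.7.2 carries sex into the bleeding models with no further edit.

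The cost is one word and one model term. No new data are needed, because the subgroup and prediction analyses already use sex. Under the assumed range the standard error of the FcγRIIa estimate rises by at most about 2%. At the 80-event minimum, events per term fall from 6.67 to 6.15.

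If sex was left out on purpose, state the reason in SAP 5.7.1 and amend protocol 9.4.2 to agree. That costs a sentence in the SAP and a protocol amendment.
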